7.2. General Methodology

Data analysis will be performed by Medtronic-employed statisticians or designees. A validated statistical software package will be used for the analyses of the study results (e.g., SAS).

This SAP is developed prior to data analysis and will include a comprehensive description of the statistical methods and reports to be included in the final study report. Any change to the data analysis methods described in the CIP will require an amendment only if it changes a principal feature of the CIP. Any other change to the data analysis methods described in the CIP, and the justification for making the change, will be described in the clinical study report.

7.3. Center Pooling

The investigators of this study will conduct the study according to a common protocol and use the same CRFs to collect study data. The site study personnel will be trained prior to the study initiation at each site. Periodic study monitoring by Medtronic will ensure compliance with protocol requirements.

There is no a priori provision to exclude any sites from the analysis. The data from all sites will be pooled for analysis. To reduce the possibility of atypical results from a site overly influencing the combined results, no more than 30 subjects will be enrolled at each site.

7.4. Handling of Missing, Unused, and Spurious Data and Dropouts

Missing data are a potential source of bias when analyzing study data. A rigorous study design and execution will help prevent the incidence of missing data from occurring.

The analysis of the primary and secondary objectives will use subjects who provide data. The purpose of the study is to characterize the minimum amplitude that maintains SCS therapy satisfaction and overall pain relief; in case subjects drop out during follow-up, the percentage of amplitude prior to dropout will be used to summarize the minimum amplitude.

7.5. Adjustments for Multiple Comparisons

As there is no hypothesis testing, adjustment for multiple endpoints is not required.

7.6. Demographic and Other Baseline Characteristics

Demographics and baseline characteristics will be summarized in the report for all subjects who complete the Baseline visit and meet the Baseline eligibility requirements.

7.7. Treatment Characteristics

Subjects are implanted before enrolling into the study, so the surgical procedures are not described in the study. The neurostimulator and lead(s) model will be summarized. Subjects proceed beyond baseline visit will receive 4 different programmed amplitude setting in the following order: 80%, 60%, 40%, and 20% of perception threshold amplitude, each for approximately two weeks. Subject assessments are collected at each following up visit.

Subjects' pain medications will be collected. All pain medications will be coded using the appropriate version of the World Health Organization (WHO) Drug Dictionary at the appropriate Anatomical Therapeutic Chemical (ATC) level.

7.8. Interim Analyses

There is no planned interim analysis for the primary and secondary objectives in this study.

7.9. Evaluation of Objectives

7.9.1. Primary Objective

To characterize the minimum amplitude as a percentage of perception threshold that maintains SCS therapy satisfaction.

7.9.1.1. Hypothesis

There is no hypothesis testing for the primary objective. The purpose of the primary objective is to characterize the minimum amplitude that maintains SCS therapy satisfaction.

7.9.1.2. Experimental Design

The measurement of SSA is described in Section 5.2.1.1. Subject dissatisfaction with the therapy is defined as subjects choosing either 'somewhat unsatisfied' or 'very unsatisfied'. The SSA is collected at baseline and scheduled follow-up visits.

A large black rectangular redaction box covers the bottom portion of the page.

7.9.1.3. Analysis Methods and Presentation Format

The frequency and percentage of subjects satisfied with the therapy will be summarized at baseline and scheduled follow-up visits. In case subjects drop out during follow-up, a category of missing data will be included in the summary so that the percentage is not inflated because of missing data. As an additional analysis, if a subject drops out of the study due to dissatisfaction with the therapy, the subject will be treated as dissatisfied (same level at dropout) at the subsequent lower percentages of amplitude where data was not collected

The percentage of amplitude from perception threshold for maintaining subjects' satisfaction with the therapy will be summarized too. In case subjects drop out during follow-up, the percentage of amplitude prior to subject dropout will be used as the minimum amplitude in the summary.

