8.5. Baseline Eligibility Criteria

To proceed on with the Baseline visit, the subject must meet the following inclusion criteria:

1. Has an average overall VAS pain score \leq 4 based on the Baseline diary

To proceed on with the Baseline visit, the subject must not meet any of the following exclusion criteria:

1. Has provided response to Baseline SSA as “Neutral”, “Somewhat unsatisfied”, or “Very unsatisfied” with the therapy
2. Completed less than 5 of the 7 days of the Baseline diary

9. Study Procedures

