9.10. Subject Withdrawal or Discontinuation

A subject has the right to withdraw from the study at any time and for any reason without prejudice to their future medical care by the principal investigator or institution. Subjects will be provided standard medical care by their physician after their study participation ends.

The study sample size accounts for expected attrition, thus exited subjects will not be replaced.

Examples of reasons for study exit include the following:

- Subject death
- Subject lost to follow-up
- Subject voluntarily withdraws from the study
- Subject becomes pregnant
- Investigator terminates the subject's participation in the study due to lack of compliance, violation of/change in eligibility criteria
- Any clinical laboratory abnormality, inter-current illness, or other medical condition or situation occurs such that continued study participation would not be in the best interest of the subject
- Normal study completion

A study exit eCRF will be completed for all enrolled subjects; the reason for withdrawal shall be recorded on the study exit eCRF. If a subject exits from the study prior to normal completion, the eCRFs for visits that have occurred up to the point of withdrawal as well as the study exit eCRF should be completed. If a subject exits due to an adverse event or device deficiency, the appropriate event eCRFs should also be completed.

If the subject proceeds beyond the Baseline/Programming Visit #1 but chooses to withdraw from the study early; if they are willing, the Final Study Visit procedures may be completed prior to study exit.

If a subject requires a system modification or replacement during the study, they should be exited from the study.

In the case that the subject is determined to be lost to follow-up, details of a minimum of two attempts and the method of attempt (e.g., one letter and one phone record or two letters) to contact the subject must be recorded in the subject's medical records. In addition, regulations set forth by the governing IRB must be followed.

10. Risks and Benefits

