10.1.1. Foreseeable Risks

10.1.1.1. Spinal Cord Stimulation Adverse Events Summary

The implantation of a spinal cord stimulation system involves risks that are similar to other spinal procedures. In addition to those normally associated with surgery, implantation or use of a

neurostimulation system includes, but is not limited to, the following risks:

- Allergic or immune system response to the implanted materials
- Infection
- Lead, extension, or neurostimulator erosion through the skin or migration
- Leakage of cerebrospinal fluid
- Loss of pain relief may return patients to their underlying pain condition
- Patients on anticoagulation therapies may be at greater risk for postoperative complications such as hematomas that can result in paralysis
- Persistent pain at the neurostimulator site
- Placement of the epidural lead-extension is a surgical procedure that may expose patients to risks of epidural hemorrhage, hematoma, or paralysis
- Radicular chest wall stimulation
- Seroma or hematoma at the neurostimulator site
- Stimulation-dependent gastrointestinal symptoms such as diarrhea, incontinence or constipation
- Stimulation-dependent bladder symptoms such as urinary retention, incontinence or frequency
- Change in stimulation, possibly related to cellular changes around the electrode(s), shifts in electrode position, loose electrical connections, lead or extension fractures, which has been described by some patients as uncomfortable stimulation (jolting or shocking sensation).
- Formation of reactive tissue around the lead in the epidural space can result in delayed spinal cord compression and paralysis, requiring surgical intervention. Time to onset can range from weeks to many years after implant.
- The safety and effectiveness of this therapy has not been established for pregnancy, unborn fetus, or delivery. The study procedures may involve unknown risks for female subjects, their embryo or fetus (unborn child), or delivery if they become pregnant. For this reason, pregnant females have been excluded from participating in this study. Female subjects must agree to not become pregnant during the study by using a medically acceptable method of birth control; an identified pregnancy will result in immediate study withdrawal.

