7.9.2.3. Analysis Methods and Presentation Format

The mean and standard deviation of the pain scores (including overall, back, and leg pain) will be summarized at each follow-up visit. The change in pain scores will be summarized too. As an additional analysis, if a subject drops out of the study due to dissatisfaction with the therapy, the subject's pain scores at dropout will be used at the subsequent lower percentages of amplitude where data was not collected

The percentage of amplitude from perception threshold for maintaining overall pain relief will be summarized. In case subjects drop out during follow-up, the percentage of amplitude prior to subject dropout will be used as the minimum amplitude in the summary.

In addition, a repeated measure analysis may be applied to examine the relationship between the change in pain score and percent amplitude. The dependent variable will be the change in pain score,

the independent variables will be percent amplitude and visit as fixed effects, and subject as the random effect. The interaction term of percent amplitude by visit will be tested and kept out of the model if it is not significant.

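### The two additional dropout analyses act only on exit for dissatisfaction, so a subject who leaves because pain relief was lost may be left out of both

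*SAP*

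**What the plan says.** SAP 7.9.1.3 handles a subject who leaves during titration in three ways.

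- **Main satisfaction table.** For any dropout, whatever the reason, "a category of missing data will be included in the summary so that the percentage is not inflated because of missing data".
- **Additional satisfaction analysis.** Here, "if a subject drops out of the study due to dissatisfaction with the therapy, the subject will be treated as dissatisfied" at the later, lower amplitudes, at the level held at dropout.
- **Minimum-amplitude summary.** "In case subjects drop out during follow-up, the percentage of amplitude prior to subject dropout will be used as the minimum amplitude in the summary". The exit reason plays no part.

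SAP 7.9.2.3 puts the same condition on the pain scores: "As an additional analysis, if a subject drops out of the study due to dissatisfaction with the therapy", the scores at dropout stand in at the lower amplitudes.

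SAP 7.9.1.2 defines dissatisfaction by the SSA answer (somewhat or very unsatisfied). It does not say how dissatisfaction is established as the cause of an exit.

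On the protocol side:

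- Section 9.10 gives examples of exit reasons. They include voluntary withdrawal, investigator termination, and a medical condition or situation that makes continuing not in the subject's interest. Neither dissatisfaction nor lack of relief is listed.
- Section 9.10 also provides for exit because of an adverse event, has the exit reason recorded on the study exit eCRF, and leaves the Final Study Visit procedures, which include the SSA, to the subject's willingness on early exit.
- Section 10.1.1.6 gives inadequate pain relief as an example of why a subject might withdraw.
- Section 10.1.1.1 lists the risk "Loss of pain relief may return patients to their underlying pain condition", and 11.3 counts therapy-related worsening of a pre-existing condition as an adverse event.

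**The concern.** The design lowers amplitude in fixed steps, and protocol 10.1.1.5 expects some subjects to lose effective therapy below a certain level. Exits for that reason are informative: the subject is unobserved at the lower settings because the higher one failed. The two additional analyses are the SAP's only safeguards that take the reason for exit into account.

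Their trigger does not match the wording the protocol uses for the exit it foresees. Dissatisfaction and loss of relief usually go together, but they are not the same thing, and only the first is named. A subject who withdraws because pain returned, or who exits for a therapy-related pain adverse event, may have no dissatisfied SSA answer on record, since that assessment is optional at early exit. Whether the subject counts would then depend on how each site describes the exit.

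The mismatch matters most for pain. The satisfaction table keeps missing subjects in the denominator. A mean has no such protection, because a subject without a carried-forward score is simply absent from it. It is also odd that a pain analysis should be triggered by dissatisfaction and not by inadequate relief.

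**Working it through.** **The plan's own figure.** The only planning number is at least 40 subjects beyond Baseline out of about 60 enrolled (protocol 13.1.1, SAP 6). It comes with no formula, precision target or dropout rate, so there is nothing to reproduce, and it is not in dispute.

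**Inputs**

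- From the documents: N = 40 treated.
- Assumed: 8 subjects leave because relief was lost, all before the 20% assessment; the other 32 give data at 20%; 24 of the 32 are satisfied and 8 dissatisfied; pain at exit is 3 points above the mean of the 32 who remain.
- Varied: k, the number of the 8 whose recorded reason does not meet the SAP trigger.

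**Formulas for the additional analyses at 20%**

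- Satisfied = 24/40
- Dissatisfied = (8 + 8 − k)/40
- Missing = k/40
- Mean pain above that of the 32 who remain = 3 × (8 − k)/(40 − k)
- Shortfall = value at k = 0 minus value at k

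| k | Satisfied | Dissatisfied | Missing | Mean pain above remainers | Shortfall |
|---|---|---|---|---|---|
| 0 | 60% | 40% | 0% | 3 × 8/40 = 0.600 | 0 |
| 2 | 60% | 35% | 5% | 3 × 6/38 = 0.474 | 0.126 |
| 4 | 60% | 30% | 10% | 3 × 4/36 = 0.333 | 0.267 |
| 6 | 60% | 25% | 15% | 3 × 2/34 = 0.176 | 0.424 |
| 8 | 60% | 20% | 20% | 0 | 0.600 |

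**What this shows**

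1. Each exit outside the trigger moves 1/40 = 2.5 percentage points from dissatisfied to missing. For k of 2 to 6 that is 5 to 15 points.
2. The percentage satisfied stays at 60% throughout, because missing subjects remain in the base.
3. For k of 2 to 6, mean pain in the additional analysis is about 0.13 to 0.42 points too low. The shortfall is proportional to the assumed 3-point gap; a 1-point gap would give 0.126/3 = 0.04 to 0.424/3 = 0.14.
4. At k = 8 the additional analysis equals the main one and protects against nothing.
5. With 4 or 12 exits in place of 8 (still 24 satisfied), and all of them outside the trigger, dissatisfied falls from 40% to 30% or 10%.
6. The minimum-amplitude summary uses the amplitude before dropout for every dropout, so k does not affect it.

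**The case against.** The strongest reply is that the SAP trigger is a cause, not a code on a form. Voluntary withdrawal says who ended participation; dissatisfaction says why. A subject who withdraws voluntarily because of dissatisfaction meets the SAP's wording. The list in 9.10 is only of examples, so a site may record dissatisfaction. SAP 7.1.1 summarizes discontinuation reasons, an adverse-event exit needs its own event form with relatedness classified, and the SSA asks the reason for the answer given. The exit eCRF is not among the documents, and there is a redaction just before 7.9.1.3, so such an item may already exist.

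This stands in part. It rules out saying that a voluntary withdrawal can never trigger the rule. It does not settle whether inadequate relief counts as dissatisfaction, who decides, or what happens to a pain-related adverse-event exit.

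It is also fair that these are additional analyses in a descriptive feasibility study. A reader might infer that the narrow trigger is what sends these subjects to missing in the main satisfaction table, or that it inflates the percentage satisfied. Neither follows: in the main table every dropout is missing whatever the reason, and missing subjects stay in the base.

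A reader might also infer that sites could remove subjects for reaching the endpoint, because 9.10 allows investigator termination "due to lack of compliance, violation of/change in eligibility criteria" and 8.5 includes a pain ceiling ("Has an average overall VAS pain score" of at most 4) and a satisfaction requirement. The documents do not support this. Those criteria are conditions for proceeding with the Baseline visit, and protocol 9.4 says eligibility is assessed through that visit. The secondary endpoint itself allows a rise of up to 2 points, so a subject entering at 4 could reach 6 and still be maintaining relief. Willingness to keep pain medication stable (8.3) does run into follow-up, but 9.5 has medication changes collected and states no exit.

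**Conclusion.** The point holds for the two additional analyses and no further. Their trigger is narrower than the exits the protocol itself foresees, and neither document closes the gap. The 2.5 points per exit follows directly from 40 treated subjects. The 5 to 15 points, and the 0.13 to 0.42 points of mean pain, rest on assumed counts and an assumed 3-point gap. The documents give no dropout rate and no split by reason, so how many exits would be affected cannot be derived; a reader who supposes there will be many has no source for it. No stated figure in the plan is wrong. The change is still worth making: it is cheap, the pain endpoint calls for a trigger based on pain relief, and the reason for an exit is hard to recover afterwards.

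**What to change.** 1. **Study exit eCRF.** Unless the form already has it, add one yes/no item for every exit whatever the main reason: was insufficient pain relief or dissatisfaction with the therapy a reason? Record the amplitude setting in force at exit.
2. **SAP 7.9.1.3 and 7.9.2.3.** Trigger both additional analyses on a yes to that item, or on exit for a therapy-related pain adverse event. The main table, the minimum-amplitude rule and the conduct of the study stay as they are.

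The cost is one form item and one sentence in each of two SAP sections. The additional results may become slightly less favourable to the low amplitudes.

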4.1. Primary Objective

To characterize the minimum amplitude as a percentage of perception threshold that maintains SCS therapy satisfaction.

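### In the readable text, the per-subject minimum amplitude is undetermined for completers with non-monotone answers or no satisfied level, and the dropout rule can credit a level that failed

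*SAP*

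**What the plan says.** The primary objective (SAP 4.1) is "To characterize the minimum amplitude as a percentage of perception threshold that maintains SCS therapy satisfaction". Subjects who pass Baseline receive "80%, 60%, 40%, and 20% of perception threshold amplitude, each for approximately two weeks", in that fixed descending order (SAP 7.7), and rate satisfaction once per level.

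SAP 7.9.1.3 gives two primary summaries. The first is by visit: "The frequency and percentage of subjects satisfied with the therapy will be summarized at baseline and scheduled follow-up visits", with a missing-data category so that dropout does not inflate the percentage. The second is the per-subject quantity, "The percentage of amplitude from perception threshold for maintaining" satisfaction, which is only said to be summarized. Its one assignment rule concerns dropouts: "the percentage of amplitude prior to subject dropout will be used as the minimum amplitude in the summary".

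An additional analysis of the by-visit table covers subjects who leave because of dissatisfaction: "the subject will be treated as dissatisfied (same level at dropout) at the subsequent lower percentages of amplitude where data was not collected".

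SAP 7.9.1.2 supplies the outcome definition: "Subject dissatisfaction with the therapy is defined as subjects choosing either" of the two unsatisfied answers. A blacked-out area follows. SAP 7.9.1.4 sets the population as the treated analysis set, meaning everyone who passes Baseline and receives at least one setting.

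The pain objective follows the same pattern in SAP 7.9.2.3: "The percentage of amplitude from perception threshold for maintaining overall pain relief will be summarized", with the same dropout sentence. Neither that section nor Protocol 13.3.2-13.3.3 shows a redaction mark, and neither states a per-subject rule.

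**The concern.** Three groups of subjects are affected.

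- **Non-monotone completers.** No step down depends on the previous answer, so a subject can fail at one level and be satisfied at a lower one. *Minimum* can be read as the lowest level with a satisfied answer. *Maintains* points to the last level before the first failure. The readable text does not choose.
- **Completers satisfied at no level.** They have no amplitude to summarize under either reading, although SAP 7.9.1.4 includes them. Tabulating only the available percentages would drop them and make the distribution conditional on success.
- **Dropouts.** A subject who is unsatisfied at 80% and leaves apparently receives 80%, a level that did not maintain satisfaction. The additional by-visit analysis would carry the same subject forward as dissatisfied.

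The lowest-satisfied reading, and dropping total failures, both lower the reported minimum. With no hypothesis test, this distribution is a main product of the study, and characterizing it is the stated reason for 40 subjects (SAP 6). An unstated rule could be settled after the data are seen.

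**Working it through.** **Plan figure.** There is none to reproduce: the 40 subjects come with no formula, rate or precision target.

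**Step 1: all possible completer sequences.** Write S for satisfied and U for unsatisfied at 80, 60, 40 and 20%. There are 2^4 = 16 sequences.

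- 5 are monotone (SSSS, SSSU, SSUU, SUUU, UUUU), and the two readings agree on them.
- 16 - 5 = 11 are non-monotone, and the readings disagree on all 11.
- 8 sequences start with U. Of these, 7 have a value under lowest-satisfied but none under first-failure, and 1 (UUUU) has none under either.

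| Sequence | Lowest satisfied | Last before first failure |
|---|---|---|
| S S S U | 40% | 40% |
| S U S S | 20% | 80% |
| U S S S | 20% | none |
| U U U U | none | none |

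**Step 2: dropouts.** For U then exit, the dropout sentence read literally gives 80%, but no tested level maintained satisfaction. For S, U then exit, it gives 60%, but the last maintained level is 80%.

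**Step 3: illustrative size.** The documents give no satisfaction rates or within-subject correlation, so these are assumptions. The model is logit P(satisfied at level k) = a_k + b, with b ~ N(0, s²) shared within subject. Each a_k is set so that marginal satisfaction is 85/75/65/55% at 80/60/40/20%. There is no dropout, and s runs from 1.5 to 4.

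| Result | s = 1.5 | s = 4 |
|---|---|---|
| Non-monotone | 30% | 11% |
| No value, lowest-satisfied | 5% | 12% |
| No value, first-failure | 15% | 15% |
| Minimum = 20%, lowest-satisfied, all subjects | 55% | 55% |
| Minimum = 20%, first-failure, all subjects | 36% | 49% |
| Median, lowest-satisfied, failures ranked above 80% | 20% | 20% |
| Median, first-failure, failures ranked above 80% | 40% | 40% |

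Two rows are fixed by the assumed marginals. Lowest-satisfied puts exactly the 55% who are satisfied at the bottom level at 20%. First-failure gives no value to 1 - 0.85 = 15%. In 40 subjects, 11-30% non-monotone is 0.11 × 40 = 4.4 to 0.30 × 40 = 12, so about 4 to 12. At s = 1.5 the first-failure median only just reaches 40% (35.9% + 14.6% = 50.5% at or below 40%).

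Means among subjects with a value are about 34 (lowest-satisfied) against 37-44 (first-failure). They exclude different subjects under each rule, so the all-subject shares and medians are the fairer comparison.

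**Step 4: more favourable rates.** With 95/90/80/60%, non-monotone subjects are 5-16% and the gap in conditional means is about 1-5 points.

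**Step 5: boundary case.** Take 40 monotone subjects, all satisfied at 80%, with minima 20/40/60/80% in 16/8/8/8. Every rule gives mean (16×20 + 8×40 + 8×60 + 8×80)/40 = 1760/40 = 44.0 and median 40.

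**The case against.** The strongest objection is the blacked-out area after the dissatisfaction definition, where a derivation rule could sit. Protocol silence is weak evidence against that, because Protocol 13.1 leaves the full methods to the SAP. This stands as a limit on wording: a reader might infer that the plan has no rule at all, and for the primary objective the documents cannot show that. It does not remove the point, because SAP 7.9.2.3 has no redaction mark and leaves the same gap for pain.

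A reader might also infer that every subject unsatisfied at 80% lacks a value. That is too broad. Those who then leave do get one under the dropout sentence; their problem is that the value credits a failed level. Nor does everyone necessarily complete four steps: Protocol 10.1.1.6 allows withdrawal for insufficient relief, which would remove some reversals. The illustration has no dropout.

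The two readings are not equally natural. *Maintains*, a descending order and a satisfied baseline lean toward first-failure. That is a reason to write it down, although one isolated unsatisfied answer would then override later satisfied ones.

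Finally, the study is descriptive feasibility work, and the by-visit table needs no minimum-amplitude rule. That part of the primary result is sound.

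**Conclusion.** The point holds in a limited form and should be settled before the analysis. In the readable text, the minimum is undetermined for non-monotone completers and missing for completers satisfied at no level, although the analysis set includes them. The dropout sentence can record a failed level as the minimum that maintained satisfaction. The same data can therefore give different primary and secondary summaries.

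The size depends on response patterns that the documents do not supply. Under the 85/75/65/55% assumption it is a median of 20% against 40%; under better rates it is a few points. It would be too strong to say that the results will differ: they need not, and with monotone answers and everyone satisfied at 80% they do not. No test, alpha or power is affected.

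**What to change.** In SAP 7.9.1.3 and 7.9.2.3:

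1. Add an ordered category *not maintained at 80%*. Keep those subjects in the treated-set denominator, and report counts and cumulative percentages over the five categories.
2. Define the minimum as the last amplitude in the descending sequence before the first failure. Give the lowest-satisfied version (for pain, the lowest level with relief maintained) as a sensitivity analysis, with the number of non-monotone subjects.
3. Amend the dropout sentence so that the amplitude before dropout counts as the minimum only if satisfaction, or pain relief, was maintained there. Otherwise use the last maintained level or *not maintained at 80%*.
4. State how a follow-up *Neutral* answer is classed. It is outside the dissatisfaction definition, yet at Baseline it excludes a subject.

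If the blacked-out text already holds a rule, check it against these four items. The cost is some SAP text, an extra table row and a sensitivity table, with no new data or visits. The reported minimum would be somewhat less favourable.
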